## **9.3 Planned efficacy/outcome analyses**

As efficacy is not evaluated in this study, there is no primary efficacy endpoint.

## **9.4 Planned outcome analyses**

### **9.4.1 Primary endpoint analyses**

The PK analyses will be performed on the PKS.

Following  $\log_e$ -transformation, the primary PK parameters ( $C_{\max}$ , area under the plasma concentration-time curve from time zero to the last quantifiable concentration [ $AUC_{(0-t)}$ ], and AUC) will each be evaluated according to an analysis of variance (ANOVA) model with a fixed effect term for pair and treatment. The estimate of the ratio of geometric mean for the AI-2mL (test) versus 2xbimekizumab-AI-1mL (reference) treatment along with the associated 90% confidence intervals (CIs) for the ratio will be calculated. Bioequivalence will be concluded if the 90% CIs for the ratio of the comparison is fully included in the acceptance range from 0.8 to 1.25 for AUC,  $AUC_{(0-t)}$ , and  $C_{\max}$ .

Two sensitivity analyses will add 1) the main effect of center and 2) both main effect of center and center-by-treatment interaction. Further sensitivity analyses may also be performed on the PK parameters.

### **9.4.2 Secondary endpoint analyses**

Additionally, a similar ANOVA will be also performed on  $\log_e$ -transformed  $t^{1/2}$  to compare elimination characteristics between treatment groups. The point estimate and the 90% CI for the median treatment differences for  $t_{\max}$  will be computed according to the Hedges Lehmann's method.

## **9.5 Planned safety and other analyses**

### **9.5.1 Safety analyses**

All safety parameters will be listed by study participant and treatment group using the Safety Set. The incidence of TEAEs will be determined by treatment group, where applicable. Absolute and relative frequencies for a given TEAE by preferred term as per the Medical Dictionary for Regulatory Activities (MedDRA®, version 19.0) will be determined within each treatment group and system organ class. Additional tables will summarize TEAEs by maximum event intensity and causal relationship with IMP per treatment group and overall. The actions taken for each

TEAE, the time of onset of the TEAE after dosing, and the duration of each AE will be listed. The TEAEs leading to discontinuation and SAEs will also be summarized.

For continuous laboratory variables, values and changes from Baseline will be summarized at each time point. For categorized values according to the reference range, shift tables from Baseline to each postdose time point will be presented for selected variables. Values outside the reference range will be flagged in the data listings. The reference ranges will be reported.

Normal versus abnormal findings for the various ECG parameters and overall ECG will be analyzed as required, focusing on the identification of outliers and of any trends for changes following administration of IMP with respect to QT/QTc. Descriptive statistics will be presented for ECG value and changes from Baseline over time.

Descriptive statistics will be reported for all vital sign measurements (including systolic and diastolic BP, pulse rate, and tympanic body temperature). Measured values and changes from Baseline will be summarized for all study participants by time point.

Abnormal findings in the physical examination will be presented in listings only.

### **9.5.2 Immunogenicity analyses**

Bimekizumab ADAb levels will be listed per participant and summarized using summary tables and figures. The number (and percentage) of study participants with first occurrence of treatment-induced ADAb positivity will also be summarized at each postdose visit.

### **9.5.3 Other analyses**

#### **9.5.3.1 Study participant disposition and characteristics**

The number of study participants who were enrolled and randomized into the study, in each analysis set, and who completed or prematurely discontinued the study, as well as the reason for discontinuation, will be presented by treatment and overall using frequency counts and percentages. In addition, listings will be provided for study discontinuation, study participant disposition, and participant analysis sets.

Study participant characteristics will include a summary and listing of the following:

- Demographics (including sex, age, race, ethnicity, height, weight, BMI, and lifestyle)
- Medical history
- Prior and concomitant medications

Concomitant medical procedures will only be listed.

### **9.6 Handling of protocol deviations**

No protocol deviation is permitted, either in retrospect or prospect.

Important protocol deviations are identified as part of the data cleaning process in the Data Cleaning Plan (DCP). The objective of the data cleaning meeting will be to review and update (if necessary) the important protocol deviations in the DCP and discuss exclusion of study participants from analysis populations.

Furthermore, overall trends in protocol deviations will be discussed at the Data Evaluation Meeting. Through this data cleaning and evaluation process, all decisions regarding important

protocol deviations and exclusions from analysis populations will be made. Protocol deviations (eg, missing assessments or visits) related to COVID-19 may be listed separately.

Accepted deviations from theoretical time points will be described in the appropriate documents and included in the trial master file (TMF).

After resolution of all issues, and documentation of all decisions, the database will be locked.

### **9.7 Handling of dropouts or missing data**

There will be no special procedures for handling missing data. All imputation of missing or partial dates for safety assessments, as well as handling values below the limit of quantification in the PK data, will be detailed in the SAP.

### **9.8 Planned interim analysis and data monitoring**

No formal interim analysis is planned for this study.

### **9.9 Determination of sample size**

This is a BE study to compare the PK of bimekizumab-AI-2mL (test) versus bimekizumab-AI-1mL (reference).

The sample size estimation was based upon variability observed in studies UP0033 and UP0068. These were the 2 most recent studies which included the AI device with a single administration of bimekizumab in healthy study participants. The respective inter-participant variabilities (coefficient of variation [CV%]) observed in these studies were up to 32%, 33% (AUC) and 31%, 25% (Cmax). The geometric mean ratios for all primary PK parameters were between 0.97 and 1.02 (UP0033) and between 1.03 and 1.15 (UP0068). The individual study CV% and geometric mean ratios are presented in Appendix 11 (Section 10.11).

Assuming a geometric mean ratio of 1.08 (or 0.93) and inter-participant variability (CV%) of 32%, 54 study participants per group are required to assess BE with 80% power assuming that BE will be declared if the 90% CI for the geometric mean ratio is contained entirely within the acceptance range (0.8, 1.25).

Sample size estimation was performed using SAS software (version 9.4).

Assuming a dropout rate and non-evaluable study participants of approximately 10%, 60 study participants per group for a total of approximately 120 study participants are to be enrolled in the study.

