## 4 STUDY DESIGN

### 4.1 Overall design

This is a Phase 1, open label, randomized, parallel-group, single dose, 2-arm BE study to compare the PK of bimekizumab 320mg when administered as either a 1x2mL or 2x1mL sc injection in healthy male and female study participants using an AI presentation. The 2 arms will be:

1. Bimekizumab-AI-2mL (test)
2. 2xBimekizumab-AI-1mL (reference)

The aim of this study is to demonstrate the BE of bimekizumab administered as either 1x2mL or 2x1mL sc injections using the bimekizumab-AI presentation in healthy study participants.

Approximately 120 healthy male and female study participants will participate at a maximum of 2 centers in the study (approximately 60 study participants in each of 2 arms). Enrollment between the 2 sites will be balanced, with an approximate 1:1 ratio. Each study participant will receive a single dose administration of bimekizumab 320mg, as either 1x2mL or 2x1mL sc injections.

Each eligible study participants will be matched with another participant for gender and body weight prior to randomization. The intention is that the body weights in each pair should differ by  $\leq 10\text{kg}$ . Ideally, the participant's body weight at admission (Day -1) should be used for pairing. One participant within each pair will be randomly allocated to receive 1 of the 2 treatments; the other participant will be allocated to the other treatment.

The duration of the study will be approximately 168 days, including 27 days of Screening, admission on Day -1, an inhouse Treatment Period from Day 1 to Day 3, Outpatients Visits until Day 112, and a SFU Visit on Day 140. Randomization will occur on Day 1 prior to dosing.

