### **6.3           Measures to minimize bias: randomization and blinding**

This is an open-label study.

A PAREXEL Biostatistician (or designee) will write the randomization plan, program and will provide a dummy output of the randomization lists for review and approval in order to ensure compliance to study requirements.

Study participant treatment assignment will be random throughout the study. Study participants will be randomized in a 1:1 ratio to each treatment group as described in Section [4.1](#).

Copies of each site's randomization list will be sent to the respective site before the start of the study to the following recipients:

- ClinBase™ setup designer
- Sponsor Drug Safety staff for SAE reporting
- Bioanalytical staff
- Site pharmacist and Pharmaceutical Services staff (for dispensing IMP)

Pharmacokinetic concentration data will not be available to the study team until after the last scheduled procedure for the last study participant in the study, so the decision to replace participants who dropped out or are missing PK visits can be made in an unbiased manner.

At the Screening Visit, each study participant will be assigned a unique 5-digit number from a range of numbers supplied by UCB. Once the Investigator determines that the study participant is eligible for the study, the study participant will be paired to another eligible study participant, matching by gender and bodyweight ( $\leq 10\text{kg}$  difference between the 2 participants) and manually assigned to the next 2 available randomization numbers by the Investigator or designee prior to dosing on Day 1. Ideally, the participant's body weight at admission (Day -1) should be used for pairing. Allocating in pairs will improve the precision of the comparison between treatments. Each specific randomization number will identify the pair a study participant belongs to and is tied to the treatment allocation on the randomization schedule, which can then be dispensed by the site pharmacist. This randomization number will also be recorded in the eCRF (ie, ClinBase; see Section 10.1.6).

Participants who withdraw from the study may be replaced at the discretion of the Investigator and Sponsor. Any replacement must match the gender and weight ( $\leq 10\text{kg}$  difference between the 2 participants) of the remaining participant being replaced and receive the same treatment as the participant being withdrawn from treatment.

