## 10.11 Appendix 11: Sample size estimation parameters

Study	Formulation	Parameter	CV%	GeoMean ratio	Comments
UP0033 n=63 per arm	SS 1mL	AUC	31.1	97.8	vs TN 1mL, CV% is from individual comparisons data
		C max	28	96.5	vs TN 1mL, CV% is from individual comparisons data
	AI 1mL	AUC	29.9	102	vs TN 1mL, CV% is from individual comparisons data
		C max	22.9	98.25	vs TN 1mL, CV% is from individual comparisons data
	TN 1mL	AUC	32.1		
		C max	30.5		
UP0068 n=~18 per arm	SS 2mL	AUC	32.8	103.4	vs SS 2x1mL, Final Report, CV% is from individual comparison
		C max	25.4	104.0	vs SS 2x1mL, Final Report, CV% is from individual comparison
	AI 2mL	AUC	28.6	115.0	vs AI 2x1mL, Final Report, CV% is from individual comparison
		C max	24.7	114.3	vs AI 2x1mL, Final Report, CV% is from individual comparison

AI=auto-injector; AUC=area under the plasma concentration-time curve from time zero to infinity;

Cmax=maximum observed plasma drug concentration; CV=coefficient of variation; Geomean=geometric mean;  
SS=safety syringe; TN=True North

---

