## 3 SAMPLE SIZE DETERMINATION

This is a BE study to compare the PK of bimekizumab-AI-2mL (test) versus bimekizumab-AI-2x1mL (reference).

The sample size estimation was based upon variability observed in studies UP0033 and UP0068. These were the 2 most recent studies which included the AI device with a single administration of bimekizumab in healthy study participants. The respective inter-participant variabilities (coefficient of variation [CV%]) observed in these studies were up to 32%, 33% for AUC and up to 31%, 25% for  $C_{max}$ . The geometric mean ratios (GMRs) for all primary PK parameters were between 0.97 and 1.02 (UP0033) and between 1.03 and 1.15 (UP0068). The individual study CV% and GMRs are presented in Appendix 11 of the protocol.

Assuming a GMR of 1.08 (or 0.93) and inter-participant variability (CV%) of 32%, 54 study participants per group are required to assess BE with 80% power assuming that BE will be declared if the 90% CI for the GMR is contained entirely within the acceptance range (0.8, 1.25).

Sample size estimation was performed using SAS software (version 9.4).

Assuming a dropout rate and non-evaluable study participants of approximately 10%, 60 study participants per group for a total of approximately 120 study participants are to be enrolled in the study.

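### 54 per group gives 80% power at a ratio of 0.93 (equivalently 1.075) but 78% at the printed 1.08, where 58 per group are needed (unpaired, single parameter).

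*Protocol*

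**What the plan says.** Protocol 9.9 (Determination of sample size) sets out the planning assumptions in one sentence: "Assuming a geometric mean ratio of 1.08 (or 0.93) and inter-participant variability (CV%) of 32%, 54 study participants per group are required". The target is 80% power, and bioequivalence is declared if the 90% confidence interval for the geometric mean ratio lies within 0.8 to 1.25. SAP Section 3 carries the same statement: "Assuming a GMR of 1.08 (or 0.93) and inter-participant variability (CV%) of 32%, 54 study participants per group are required". Both documents then raise 54 to 60 per group to allow for about 10% dropouts and non-evaluable participants.

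The design behind the calculation is given in Protocol 4.1 ("This is a Phase 1, open label, randomized, parallel-group, single dose, 2-arm BE study to compare the PK") and Protocol 6.3 ("Study participants will be randomized in a 1:1 ratio to each treatment group"). Protocol Appendix 11 lists the CVs and ratios from the two earlier studies. It does not give the planning ratio to more decimals, and no other section does.

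**The concern.** The sentence attaches one sample size to two ratios, one above and one below 1. On the log scale the limits 0.80 and 1.25 are symmetric, so a single sample size serves both ratios only if they are reciprocals. These are not: 1.08 lies further from 1 than 0.93 does, so it needs more participants for the same power.

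At stake is whether the sample-size statement can be reproduced from its printed inputs. Anyone who enters 1.08, the ratio printed first, will not obtain 54. The upper side is also the natural one to check, because the earlier comparison of the 2mL with the 2x1mL autoinjector in Appendix 11 gave ratios above 1 (115.0% for AUC, 114.3% for Cmax).

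**Working it through.** **Inputs**

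- Two parallel groups, 1:1 (Protocol 4.1 and 6.3)
- CV 32%, ratio 1.08 or 0.93, power 80%, 54 per group (Protocol 9.9, SAP Section 3)
- 90% confidence interval within 0.80 to 1.25, that is, two one-sided tests at 5% each (Protocol 9.9)
- Analysis on the natural-log scale (Protocol 9.4.1)

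**Formulas**

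- Log-scale SD: σ = √ln(1 + 0.32²) = 0.3122
- Standard error of the log ratio with 54 per group: 0.3122 × √(2/54) = 0.0601
- Degrees of freedom: 2 × 54 − 2 = 106, so the one-sided 5% t value is 1.659
- Power: the probability that both one-sided tests reject, integrated over the distribution of the variance estimate. A noncentral-t calculation gave identical values.

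**Reproducing the plan's figure.** At 0.93, 54 per group gives 80.03% and 53 gives 79.36%. So 54 is the exact minimum for 0.93, and equally for its reciprocal, 1.0753.

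**The same calculation at the other ratios**

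| Ratio | Per group | Power |
|---|---|---|
| 0.93 (= 1/1.0753) | 53 | 79.36% |
| 0.93 | 54 | 80.03% |
| 1.075 | 53 | 79.48% |
| 1.075 | 54 | 80.15% |
| 1.08 (= 1/0.926) | 54 | 77.96% |
| 1.08 | 57 | 79.91% |
| 1.08 | 58 | 80.53% |
| 1.08 | 60 | 81.70% |

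**Hand check.** Only the nearer limit matters here, so power is approximately Φ(distance to the limit / SE − t).

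- At 1.08: (ln 1.25 − ln 1.08)/0.0601 = (0.2231 − 0.0770)/0.0601 = 2.43. Then 2.43 − 1.66 = 0.77, and Φ(0.77) ≈ 0.78.
- At 1.0753: (0.2231 − 0.0726)/0.0601 = 2.51. Then 2.51 − 1.66 = 0.85, and Φ(0.85) ≈ 0.80.

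**Where the 54 comes from.** The largest ratio at which 54 per group reaches 80% with CV 32% is 1.0753, which is 1/0.93.

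**Other methods.** At 1.08 and CV 32%, a normal approximation needs 57 per group. Setting the log SD equal to 0.32 needs 60. Using 53 degrees of freedom, as in a model with 54 pairs, with no gain in precision from pairing gives 77.5% at 54. None of these yields 54 at 1.08.

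**Sensitivity to the CV.** At 1.08 with 54 per group, power reaches 80% if the CV is 31.05% or less. The autoinjector rows of Appendix 11 give:

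| Row | CV | Power at 1.08, 54 per group |
|---|---|---|
| AI 1mL, AUC | 29.9% | 82.5% |
| AI 1mL, Cmax | 22.9% | 95.5% |
| AI 2mL, AUC | 28.6% | 85.2% |
| AI 2mL, Cmax | 24.7% | 92.7% |

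**The case against.** The best defence is that nothing was miscalculated. The sentence offers two ratios, 54 is exactly right for one of them, and 1/0.93 is 1.08 to two decimals, the precision used for every ratio in that section. On this view it is rounding, and no larger than the rounding of the CV: moving the CV from 31.5% to 32.5% shifts power at 0.93 from 81.1% to 79.0%. That explains how the mismatch probably arose. It does not make the sentence true for the ratio printed first. At 80.03% the sample size has no slack, so here the rounding crosses the 80% line.

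A second argument is that 78% is not the power of the planned analysis, because the primary model includes pair and the protocol expects pairing by gender and weight to improve precision. This is fair. With 54 pairs, 53 degrees of freedom and CV 32%, a within-pair correlation of about 0.07 would restore 80% at 1.08; correlations of 0, 0.10 and 0.20 give 77.5%, 81.2% and 85.1%. The documents state no correlation, so these are assumed values. The sample-size sentence does not invoke pairing, and its 54 is reproduced by the unpaired calculation. The point therefore concerns the printed statement, not the power the trial will have.

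Third, 60 per group are to be enrolled and withdrawn participants may be replaced. If all 60 were evaluable, power at 1.08 would be 81.7%. But the plan assigns the extra six to the expected 10% loss and states its 80% at 54.

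**Conclusion.** The point holds as a minor error of statement. In Protocol 9.9 and SAP Section 3, 80% power with 54 per group follows from a ratio of 0.93 (or 1.075) and not from the printed 1.08. At 1.08 the shortfall is about 2 points of power (78.0%), or 4 per group (58 instead of 54). These figures assume CV 32%, an unpaired two-group comparison, and one PK parameter at a time; joint power over AUC, AUC(0-t) and Cmax was not assessed.

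The finding does not show that the study is too small or that the paired analysis would miss 80%. That 1.08 stands for 1.075 is an inference from the exact match at 1/0.93.

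**What to change.** The sponsor should confirm which ratio was entered in the sample-size program, then correct the sentence in both documents.

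- If it was 0.93 or 1.075: print the assumption as 1.075 (or 0.93). The 54 per group is then the correct minimum for both.
- If 1.08 was meant: state that 54 per group gives 78% power at 1.08 and that 58 evaluable per group are needed for 80%. With the plan's 10% allowance, 58/0.9 = 64.4, or 65 per group. That figure is context; the correction itself does not require a change in enrolment.

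It would also help to say that the figure is for one parameter in an unpaired comparison.

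The cost is a text change in two places. Enrolment, the analysis model and the bioequivalence criterion are unaffected.

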### 5.4.2 Statistical analysis of bioequivalence

#### 5.4.2.1 Primary analysis

Following  $\log_e$ -transformation, the primary PK parameters (AUC,  $AUC_{(0-t)}$  and  $C_{max}$ ) will each be evaluated according to an analysis of variance (ANOVA) model with a fixed effect term for pair and treatment.

For comparison of bimekizumab-AI-2mL (test) versus bimekizumab-AI-2x1mL (reference) treatment, the difference between the least squares means (LSMs) will be estimated and back transformed in order to obtain the GMR and associated 90% CI for the ratio. Bioequivalence will be concluded if the 90% CIs for the ratio of the comparison is fully included in the acceptance range from 0.8 (80%) to 1.25 (125%) for AUC,  $AUC_{(0-t)}$ , and  $C_{max}$ .

All study participants in the PKS will be included in the analysis as far as the data permit; a study participant may be included in the analysis for one or more PK parameters (i.e., if it was not possible to calculate AUC for a given participant, the participant may be included in the analysis of BE for  $AUC_{(0-t)}$  and  $C_{max}$ ).

The results of the BE analysis will be tabulated, including the geometric LSMS and 95% CI for treatment group, the estimated GMR and 90% CI, and CV% for the bimekizumab-AI-2mL (test) versus bimekizumab-AI-2x1mL (reference) treatment.

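### The 80% power in Protocol 9.9 and SAP 3 is for one PK parameter, but BE requires AUC, AUC(0-t) and Cmax all to pass, so joint power at the stated inputs is below 80% unless the three results fully agree

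*Protocol*

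**What the plan says.** Protocol 9.9 sets out a single calculation: "Assuming a geometric mean ratio of 1.08 (or 0.93) and inter-participant variability (CV%) of 32" per cent. Its success condition is in the singular: "BE will be declared if the 90% CI for the geometric mean ratio is contained entirely within the acceptance range (0.8, 1.25"). The result is worded as power for the BE decision: "54 study participants per group are required to assess BE with 80% power assuming that BE will be declared if the 90% CI". The 54 evaluable participants per group are then raised to 60 for about 10% dropout or non-evaluability. SAP 3 repeats the claim: "54 study participants per group are required to assess BE with 80% power".

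The decision rule is broader. Protocol 9.4.1 requires that the interval for "the comparison is fully included in the acceptance range from 0.8 to 1.25 for AUC", and equally for AUC(0-t) and Cmax. SAP 5.4.2.1 has the same rule, with the interval "fully included in the acceptance range from 0.8 (80%) to 1.25 (125%) for AUC" and the other two parameters.

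Both documents analyse each log-transformed parameter by ANOVA with fixed effects for pair and treatment. Protocol 6.3 says that allocating in pairs improves precision but gives no figure. Protocol 9.9 and SAP 3 do not mention pairing. Neither document gives a correlation between parameters, a within-pair correlation, or the power to pass all three tests.

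**The concern.** The probability of passing three tests cannot exceed the probability of passing the hardest one. The two are equal only if every trial that passes the hardest test also passes the others. The figure given as power to assess BE therefore answers a narrower question than the one the trial will be judged on.

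This matters because UP0068 closed early and could not conclude BE for the 2mL autoinjector (Protocol 2.2). Readers of this protocol will take 80% as the chance that the present design settles the question if its assumptions hold. What is at stake is the risk of a second inconclusive study. False claims of BE are not at issue, since an all-must-pass rule does not inflate them.

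**Working it through.** **Inputs from the documents.** 54 per group, CV 32%, GMR 0.93 or 1.08, 90% CI within 0.8–1.25 (Protocol 9.9). Cmax CVs up to 31% (UP0033) and 25% (UP0068), same section. All three parameters must pass (Protocol 9.4.1, SAP 5.4.2.1).

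**Assumed inputs.** Correlation of AUC with AUC(0-t): 0.98. Correlation of Cmax with both AUCs: 0.5 to 0.9. The same GMR for all three parameters.

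**Step 1: reproduce the plan's figure for one parameter.**
Log-scale variance: ln(1 + 0.32²) = 0.0975, so SD = 0.312.
Normal approximation: n = 2 × 0.0975 × (1.645 + 0.842)² / (ln 1.25 − |ln GMR|)².
- GMR 0.93: 1.205 / (0.2231 − 0.0726)² = 53.2, so 54.
- GMR 1.08: 1.205 / (0.2231 − 0.0770)² = 56.4, so 57.

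Exact two one-sided tests power with 54 per group and 106 df is 80.0% at GMR 0.93 and 78.0% at GMR 1.08. The exact n for 80% is 54 and 58 respectively. The inflation also reproduces: 54 / 0.9 = 60. The published 54 and 80% therefore belong to one parameter at GMR 0.93.

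**Step 2: joint power, unpaired.**
Simulate the three mean log differences as multivariate normal with mean ln GMR and covariance 2Σ/54, and take the variances from a Wishart distribution with 106 df. Count a success when all three intervals, difference ± t(0.95, 106) × √(2s²/54), lie within ln 0.8 to ln 1.25. Each scenario used 100,000 to 200,000 replicates. Rounding and simulation noise can move an entry by about a point.

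| GMR | CV of AUC and AUC(0-t) | CV of Cmax | Joint power at Cmax–AUC correlation 0.5 / 0.7 / 0.8 / 0.9 |
|---|---|---|---|
| 0.93 | 32% | 32% | 67 / 70 / 71 / 74% |
| 0.93 | 32% | 31% | 69 / 71 / 73 / 75% |
| 0.93 | 32% | 25% | 75 / 76 / 77 / 78% |
| 1.08 | 32% | 32% | 64 / 67 / 69 / 71% |
| 1.08 | 32% | 31% | 66 / 68 / 70 / 72% |
| 1.08 | 32% | 25% | 72 / 74 / 75 / 75% |

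Raising the AUC–AUC(0-t) correlation to 0.99 adds about a point at the upper ends for GMR 1.08 (72% with CV 32% throughout, 76% with Cmax CV 25%). Perfect concordance gives the ceilings from Step 1: 80% and 78%.

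**Step 3: the planned pair model.**
With 54 complete pairs, the variance of the difference becomes 2σ²(1 − ρ)/54 with 53 df, where ρ is the within-pair correlation. The documents do not give ρ. Taking Cmax CV 31% and Cmax–AUC correlation 0.8:

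| Assumed ρ | Joint power, GMR 0.93 | Joint power, GMR 1.08 |
|---|---|---|
| 0 | 72% | 69% |
| 0.1 | 77% | 74% |
| 0.2 | 81–82% | 79% |

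These figures need 54 complete pairs. With pair as a fixed effect, a pair that has lost one member adds nothing to the treatment contrast. If the 10% losses fell independently and no one were replaced, the expected number of complete pairs would be 60 × 0.9 × 0.9 = 48.6.

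**The case against.** The strongest reply has four parts.

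First, nothing is miscalculated: 54 and 80% reproduce at GMR 0.93, and Protocol 9.9 states its condition for one interval. This stands as far as the arithmetic goes. It does not justify describing the result as power to assess BE when the protocol's own BE rule has three conditions.

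Second, the planned analysis is paired, and Step 3 shows that a modest within-pair correlation could bring joint power back to about 80%. This also stands, and it means that the size of any shortfall in the actual trial is not established. But the sample size section makes no use of pairing, so pairing cannot be the basis of the 80% printed there.

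Third, the planning CV is cautious. In Appendix 11 the UP0033 maxima come from the True North rows (AUC 32.1, Cmax 30.5). The autoinjector rows are lower: 29.9 and 22.9 in UP0033, 28.6 and 24.7 in UP0068. With those CVs, and the AUC value used for AUC(0-t), the unpaired method of Step 2 gives about 81–85% at GMR 0.93 and 78–83% at 1.08. This is a fair reason not to call the trial too small, but the plan chose 32% and quoted power for it.

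Fourth, withdrawn participants may be replaced, so the evaluable number could exceed 54. That is discretionary and is not in the calculation.

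A reader might be tempted to go further in three ways that the documents do not support:
- Giving one fixed joint power for the trial. That needs correlations that neither document supplies.
- Using the Appendix 11 row for the 2mL autoinjector (AUC 28.6% and 1.150, Cmax 24.7% and 1.143), where joint power is about 33–41%. Single-parameter AUC power there is already 46%, so most of the drop comes from the choice of GMR. The row rests on about 18 per arm from a study closed early.
- Treating the absence of AUC(0-t) rows from Appendix 11 as an error. It is only missing detail.

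**Conclusion.** The point holds as a mismatch between the stated power and the stated decision rule. At the inputs in Protocol 9.9, 80% is the power for one parameter at GMR 0.93, and about 78% at GMR 1.08. For the three-parameter rule at the same inputs, power is below 80% unless the results are fully concordant.

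Under the assumed correlations and an unpaired analysis, the loss from the three-part rule is about 6–13 points at GMR 0.93 (80 less 67–74) and 6–14 points at GMR 1.08 (78 less 64–72) with CV 32% throughout. It is about 2–5 and 2–6 points if Cmax CV is 25%. The direction follows from the rule itself; the size depends on correlations the sponsor can estimate and the documents do not report.

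It does not follow that the trial is underpowered or that 120 participants are too few. Pairing or a smaller CV could make up the difference, and incomplete pairs would work the other way.

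**What to change.** In Protocol 9.9 and SAP 3:

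1. Describe 80% as the power for each parameter separately, at GMR 0.93 and CV 32%, and give about 78% for GMR 1.08.
2. Replace the statement of power to assess BE with the joint power for AUC, AUC(0-t) and Cmax under the planned pair-and-treatment model, at both GMRs.
3. Take the between-parameter correlations, and any within-pair correlation that can be formed by matching on sex and weight, from the UP0033 and UP0068 individual data. State the number of complete pairs assumed.

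The illustrative ranges above should not be copied into the documents; the sponsor's own estimates should replace them. The cost is a few sentences and one short simulation on data from the two earlier studies. The stated power may become less favourable. Enrolment, the analysis model and the decision rule do not change.
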